1. OBJECTIVES

1.1 Study Design

A double-blind, randomized phase II clinical trial of brain-directed stereotactic radiation with or without AGuIX gadolinium-based nanoparticles in the management of brain metastases at higher-risk of local recurrence with radiation alone.

1.2 Primary Objectives

To evaluate the hypothesis that, among patients with brain metastases at higher-risk of local recurrence with radiation alone, AGuIX gadolinium-based nanoparticles and brain-directed stereotactic radiation will improve local control, using criteria from the Response Assessment in Neuro-Oncology (RANO) – Brain Metastasis group,¹ relative to brain-directed stereotactic radiation alone.

1.3 Secondary Objectives

To compare the following other endpoints between patients managed with AGuIX gadolinium-based nanoparticles and brain-directed stereotactic radiation versus brain-directed stereotactic radiation alone:

1. Overall survival (i.e. all-cause mortality)
2. Death due to neurologic disease progression (defined as death due to progressive brain metastases on imaging associated with progressive neurologic symptomatology in the setting of systemic disease that has not progressed to a life-threatening nature)
3. Performance status, assessed longitudinally
4. Ability to complete activities of daily living, assessed longitudinally
5. Incidence and time to detection of new brain metastases
6. Incidence and time to development of radiation necrosis
7. Incidence and time to development of leptomeningeal disease
8. Incidence and time to progressive intracranial disease
9. Incidence and time to salvage craniotomy
10. Incidence and time to additional radiotherapeutic treatments after the initial course (stereotactic or whole brain radiation)
11. Progression free survival
12. Incidence and time to the development of seizures
13. Neurocognition, assessed longitudinally
14. Quality of life, assessed longitudinally
15. Steroid use, assessed longitudinally
16. Local recurrence at one year in metastases treated radiotherapeutically using RECIST (response evaluation criteria in solid tumors) criteria

2 BACKGROUND

2.1 Study Disease(s)

Brain metastases are diagnosed in 10-50% of patients with cancer. The number of patients diagnosed with brain metastases in the United States per year is approximately 175,000, and is expected to increase over time.² Chemotherapy achieves unreliable and often poor control of brain metastases given limited penetration through the blood-brain barrier.³ Targeted therapies, such as EGFR inhibitors⁴ and ALK inhibitors⁵ in non-small cell lung cancer, HER2 targeting agents in breast cancer,⁶⁻⁸ and BRAF/MEK inhibitors⁹ or immunotherapy¹⁰ in melanoma, have shown significant promise in controlling intracranial disease but relatively few patients with brain metastases can be reliably and durably managed with systemic agents. Accordingly, brain-directed radiation represents the mainstay of therapy for most patients with brain metastases.

Increasingly, stereotactic radiation, in which only the visualized metastases are treated, is being used in lieu of whole brain radiation, given the toxicity profile of the latter therapy.^{11,12} However, select patients with brain metastases are at especially higher risk of local recurrence with stereotactic radiation alone, including patients with melanoma and progression on immunotherapy,¹³ gastrointestinal primaries,¹⁴ HER2 positive breast cancer,¹⁵ cystic brain metastases,¹⁶ larger lesions,¹⁷ and local recurrences after prior stereotactic radiation¹⁸ or whole brain radiation.¹⁹ Local recurrences after stereotactic radiation in these populations can lead to progressive neurologic symptomatology, decline in quality of life and neurocognitive function, and neurologic death.²⁰ As a result, strategies to promote radiosensitization have significant appeal in such patients.

[figure not shown]

2.2 IND Agent

The radiosensitizing agent evaluated in this study is Activation and Guidance of Irradiation by X-ray (AGuIX), developed by NH TherAguix, a gadolinium-chelated polysiloxane based nanoparticle which is intravenously injectable and visible on magnetic resonance imaging (MRI).³⁵ AGuIX nanoparticles are comprised of a polysiloxane matrix with gadolinium cyclic

chelates covalently grafted on the inorganic matrix (see Figure 1 below):

[figure not shown]
Figure 1: Representative diagram of AGuIX with a polysiloxane matrix and gadolinium chelates (green).

2.3 Rationale

Gadolinium atoms lead to formation of Auger electrons when radiated, inducing reactive oxygen species, thereby potentiating radiation effect,³⁶ as shown in Figure 2.

Figure 2. Radiosensitization by AGuIX nanoparticles

AGuIX nanoparticles accumulate in brain metastases (sites of blood-brain barrier breakdown) similar to gadolinium-based contrast agents used in diagnostic imaging and are sufficiently small (<5nm) to allow for renal clearance, typically with a blood half-life ranging between 0.8-3.0 hours.³⁷ However, unlike gadolinium-based contrast agents currently in use for MRI imaging

studies, AGuIX nanoparticles are retained within brain metastases and can be visualized on MRI days after treatment.^{38,39} AGuIX nanoparticles have especially high potential for impactful radiosensitization with brain-directed stereotactic radiation, given the uptake of gadolinium in the exact same location as the radiation target, with minimal uptake and radiation deposition to other sites of the brain.

AGuIX nanoparticles were combined with brain-directed radiation in the Nano-Rad clinical trial, in which patients received whole brain radiation in the presence of escalating doses of AGuIX. Evidence of increasing radiosensitization was seen at escalating doses of 15, 30, 50, 75, and 100 mg/kg.⁴⁰ No hemodynamic, cardiovascular, renal, hepatic, or other significant acute toxicities were noted. Of the 15 patients evaluated, no “in field” short or long-term grade IV toxicities were noted. One patient developed acute, in field, grade 3 toxicity (intracranial pressure increased); there were two in field late grade 3 toxicities (“confusional state” and “delayed effects of radiation”). In addition, 1 patient had “general physical health deterioration” that was listed as a possibly related SAE. Most SAEs on this study were felt to be related either to brain metastases, extracranial progression or other systemic treatment. Ten patients died during the follow up period of the study. Of these, nine deaths were considered not related to the experimental treatment while one death was felt to be related to disease progression with superimposed radiation related leukoencephalopathy. As a result of safety and early efficacy results, AGuIX based nanoparticles are being evaluated in multiple prospective phase II studies with 100mg/m² felt to be the optimal dose for brain-directed investigations (NCT03818386, NCT04094077) and are also being evaluated by other trials at BWH/DFCI (DFCI 19-826).

3 PARTICIPANT SELECTION

3.1 Eligibility Criteria

- 3.1.1. Participants must have a biopsy proven solid malignancy and at least one intracranial measurable lesion spanning ≥ 5 mm in maximal unidimensional size and radiographically consistent with or pathologically proven to be a brain metastasis AND meet one of the following additional criteria regarding the primary site or nature of the intracranial disease:
- Melanoma with intracranial growth consistent with tumor progression despite immunotherapy
 - Gastrointestinal primary
 - HER2 positive breast cancer (subtype assessed using most representative tissue available in opinion of enrolling clinician and/or study PI)
 - Cystic metastases
 - Metastases ≥ 2 cm in maximal unidimensional size
 - Locally recurrent metastases after prior stereotactic radiation
 - Locally recurrent metastases after prior whole brain radiation
- *Patients with metastases from melanoma, GI primaries, or HER2+ breast cancer, as well as those with cystic metastases or metastases ≥ 2 cm in maximal unidimensional size, who have local recurrences after prior brain-directed radiation can only be treated in the strata permitting prior radiation (last two strata above)*
- 3.1.2. Age ≥ 18 years at diagnosis of brain metastases
- 3.1.3. Estimated glomerular filtration rate of ≥ 60 mL/min/1.73m²
- 3.1.4. Karnofsky performance status of at least 70 (i.e. at minimum, “cares for self” but “unable to carry on normal activity or do active work”)
- 3.1.5. Estimated survival based on extracranial disease of at least 3 months in the opinion of the enrolling clinician and/or study PI
- 3.1.6. Ability to understand and the willingness to sign a written informed consent document
- 3.1.7. The effects of AGuIX on the developing human fetus are unknown. For this reason, women of child-bearing potential must agree to use adequate contraception prior to study entry and for the duration of the therapeutic component of study participation

3.2 Exclusion Criteria

- 3.2.1. Participants who cannot undergo a brain MRI
- 3.2.2. Participants who cannot receive gadolinium
- 3.2.3. Participants with widespread, definitive leptomeningeal disease
- 3.2.4. Patients requiring radiation to either >10 targets (if naïve to whole brain radiation) or >20 targets (if whole brain radiation has been given previously) per the discretion of the treating clinician and/or study PI
- 3.2.5. Pregnant women are excluded from this study because of the potential deleterious effects of gadolinium on the developing fetus. Because there is an unknown but potential risk for adverse events in nursing infants, women who are breastfeeding are

- not eligible for this study
- 3.2.6. In cohorts who have received prior brain-directed radiation, patients are not eligible for this study if they have active (at the time of protocol screening) brain metastases that require radiation that are in or within 1.0cm of the brainstem, eyes, optic nerves, or optic chiasm if the juxtaposed organ at risk (i.e. brainstem, eyes, optic nerves, or optic chiasm) has previously received either >6.0 Gy in a single fraction or, if prior radiation was fractionated, a cumulative dose in 2.0 Gy equivalents, using an alpha/beta ratio of 2, of >40.0 Gy. In addition, all patients who have had prior brain-directed radiation, regardless of technique/dose/fractionation, are not eligible for the study until written approval is provided by the study/site PI.

3.3 Inclusion of Women and Minorities

Both men and women of all races and ethnic groups are eligible for this trial.

4 REGISTRATION AND RANDOMIZATION PROCEDURES

4.1 General Guidelines for DF/HCC Institutions

Institutions will register eligible participants in the Clinical Trials Management System (CTMS) OnCore. Registrations must occur prior to the initiation of any protocol-specific therapy or intervention. Any participant not registered to the protocol before protocol-specific therapy or intervention begins will be considered ineligible and registration will be denied.

An investigator will confirm eligibility criteria and a member of the study team will complete the protocol-specific eligibility checklist.

The eligibility checklist(s) and all pages of the consent form(s) will be faxed to the ODQ at [contact]. The ODQ will (a) review the eligibility checklist, (b) register the participant on the protocol, and (c) randomize the participant.

Randomization can only occur during ODQ business hours (8:30am - 5pm Eastern Time, Monday through Friday excluding holidays).

An email confirmation of the registration and/or randomization will be sent to a secondary clinical research coordinator (secondary CRC, the unblinded coordinator listed below) immediately following the registration and/or randomization. The patient, treating clinician, primary research coordinator, research nurse, study PI, and remainder of the study team will remain blinded to the treatment assignment. The secondary research coordinator will coordinate with the pharmacy to facilitate preparation and distribution of the study agent or placebo and then have no further role in study procedures, as discussed below. The secondary research coordinator will not interact with the patient in any way.

Following registration, participants may begin protocol-specific therapy and/or intervention. Issues that would cause treatment delays should be discussed with the study PI of the registering site.

4.2 Registration Process for DF/HCC Institutions

Applicable DF/HCC policy (REGIST-101) must be followed.

4.3 General Guidelines for Other Investigative Sites

N/A

4.4 Registration Process for Other Investigative Sites

N/A

5. TREATMENT PLAN

5.1. Treatment Regimen

Blinding

The reason for blinding is that the primary endpoint (local recurrence) will be made by the study PI and a blinded study will reduce bias in this assessment. As noted in section 2 of this protocol, tumor recurrence and radiation necrosis (damage to the underlying brain secondary to radiation) are difficult to delineate. Radiographic assessment alone is insufficient; incorporation of radiation-based and clinical covariates improves the accuracy of this assessment significantly. Therefore, final delineation will be made by the study PI after incorporation of radiation-based and clinical covariates into the assessment; blinding is integral in reducing/eliminating bias. As noted above, the study team has demonstrated an ability to delineate tumor progression from necrosis with 90% accuracy using such an approach.³⁴ A similar randomized phase II study using whole brain radiation with or without AGuIX gadolinium-based nanoparticles (as opposed to the stereotactic radiation utilized in this study) is also being conducted (NCT03818386).

Consequently, patients and investigators, including the primary CRC, will be blinded as to whether AGuIX or placebo is being infused. A second, unblinded CRC will confirm the treatment arm with the unblinded pharmacist and work with the pharmacy to mask, with an opaque cover, the preparation made by the unblinded pharmacist prior to dispensing to other study personnel (as the AGuIX solution is colored). Once the infusion is completed, the infusion container will be discarded with the opaque cover in place to ensure continued blinding of all investigators and participants. To ensure complete blinding of the PI, who will be making delineations of local recurrence versus tumor progression, non-brain / non-radiation related symptomatology of minor consequence (grade 1-2 adverse effects) possibly, probably, or definitely relating to the infusion occurring during or after (i.e. within 24 hours) the infusion in patients enrolled by the study PI, will be managed by a nursing / covering physician team that will be separate from the study PI.

Treatment

Radiation will begin within 14 days of the planning MRI (obtained with standard gadolinium). All patients will receive either AGuIX (100mg/kg) or placebo (normal saline, as discussed below) injection 2-5 days before radiation initiation in order to infuse the core of the tumor with AGuIX in those assigned to receive it. A brain MRI will be performed on this date, both pre-infusion and post-infusion. For patients receiving stereotactic radiosurgery (SRS, focused radiation in 1 day) alone the next AGuIX (100mg/kg) or placebo injection will take place 1-5 hours (preferably 2 hours) before the radiation treatment; no further AGuIX / placebo injections will be given. For patients managed with stereotactic radiotherapy (SRT, focused radiation in 5 days) with or without SRS AGuIX (100mg/kg) or placebo injection will be given 1-5 hours (preferably 2 hours) before radiation treatment on day 1 of radiation and 1-5 hours (preferably 2 hours) before radiation on day 3 of radiation. Patients receiving both SRS and SRT can receive treatment over 5 or 6 days, as discussed below. In both cases, SRS should be performed on day 1; SRT would start on day 1 or day 2, respectively.

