8.1.10 Placebo

The placebo will consist of sterile normal saline. The volume of saline will mimic the volume of the AGuIX infusion in patients assigned to the experimental arm. Infusion times will be equivalent in the two cohorts. The process of masking AGuIX and the placebo is described above in section 5.1.

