
The length of follow up for the neurocognitive secondary endpoint will also be 12 months. The length of follow up for all other endpoints will be until censoring or death. Of note, the usual clinical care for patients with brain metastases involves a radiation oncology visit, history, and an MRI brain every 1.5-3 months until death or other loss to follow up. All secondary endpoints (with the exception of neurocognition and health status) are assessed as part of usual clinical care. Patients can elect to follow-up with a local provider following the completion of radiation if deemed appropriate by the study PI, in which case brain imaging must be retrieved and digitally stored. Providers will call patients whom elect to follow-up with a local provider to discuss imaging results and complete study documentation; in such cases quality of life testing and neurocognition do not need to be pursued.

Study calendars are presented here:

Patients managed with SRS

	Baseline ^a	Radiation Planning	2-5 Days Before Radiation Initiation	Radiation Day 1 ^b	Follow Up ^c	eDC Timepoints
Informed consent	X					
Medical history	X				X	Baseline
Karnofsky performance status	X				X	Baseline, Follow-up
CT simulation		X				Pre-Radiation
MRI brain			X ^d		X	Pre-Radiation, Follow-up
SRS				X		Radiation
AGuIX or placebo administration			X	X		Pre-Radiation, Radiation
Quality of life assessment	X				X	Baseline, Follow-up
Health status assessment	X				X	Baseline, Follow-up
Neurocognitive Assessment	X				X ^e	Baseline, Follow-up
Volumetric imaging	X				X	Baseline, Follow-up
AE assessment ^f	X		X ^g	X ^g	X	Baseline, Pre-Radiation, Radiation, Follow-up

Abbreviations: AE=Adverse Event; AGuIX=Activation and Guidance of Irradiation by X-ray; CT=Computed Tomography; MRI=Magnetic Resonance Imaging; SRS=Stereotactic Radiosurgery; SRT=Stereotactic Radiotherapy

a. Within 21 days

b. Within 14 days of radiation planning MRI

c. Follow up visits occur post radiation at approximately 1.5/3/5/7/9 months, and every 3 months thereafter (+/- 4 weeks except 1.5 month visit which is +/- 1 week)

d. To be performed before and after administration of AGuIX vs placebo

e. Neurocognitive assessments occur in the follow up period at 3 months and 12 months

f. For the purpose of this protocol, acute adverse events collected and documented on CRFs are only acute non-hematologic grade 3 or higher toxicities that did not predate radiation and are possibly, probably or definitely related to radiation/AGuIX

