11.1.3. Methods for Evaluation of Disease

Metastases will be measured on T1 post MPRAGE or SPGR sequences, or equivalent. MRIs acquired over the course of the study for a given patient must be fused / registered to ensure consistency of evaluation and remove imprecision related to head position / slicing during scan acquisition. Measurements will be made digitally and saved electronically for future reference. All baseline evaluations should be performed as closely as possible to the beginning of treatment as possible.

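### The protocol does not keep the post-infusion brain MRI from the study PI, who alone adjudicates the primary endpoint, so following the plan can unblind the PI

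*Protocol*

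**What the plan says.** - **Infusion and scan.** Under section 5.1 every patient receives AGuIX or placebo by "injection 2-5 days before radiation initiation in order to infuse the core of the tumor with AGuIX in those assigned to receive it". For the same day it adds: "A brain MRI will be performed on this date, both pre-infusion and post-infusion". All three study calendars in section 10 carry this MRI; the SRS calendar's footnote reads "To be performed before and after administration of AGuIX vs placebo".
- **What the scan can show.** Section 2.2 describes AGuIX as visible on MRI. Section 2.3 says it accumulates in brain metastases much as diagnostic gadolinium contrast does, and that "AGuIX nanoparticles are retained within brain metastases and can be visualized on MRI days after treatment". Section 8.1.10 states: "The placebo will consist of sterile normal saline".
- **Who decides the endpoint.** Under 11.1.5 and 11.1.7 the study PI makes all final determinations of recurrence, and growth that the PI attributes to necrosis is not an event. Section 5.1 holds imaging alone insufficient for this call and says that "blinding is integral in reducing/eliminating bias".
- **How blinding is protected.** Section 5.1 gives two measures: an opaque cover, because the solution is coloured, and a separate team for grade 1-2 infusion-related events in patients whom the PI enrolled. Section 11.1.5 calls the PI blinded by reference to these procedures.
- **Image handling.** Section 11.1.3 says: "MRIs acquired over the course of the study for a given patient must be fused / registered". It makes no exception for the infusion-day scans.

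**The concern.** The protocol guards against weak clues to allocation and leaves a potentially strong one open. A pair of scans around an infusion of either an MRI-visible agent or saline can act as a test of which was given.

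This matters because the primary endpoint turns on one person's judgement between recurrence and necrosis. If that person knows or suspects the arm, necrosis calls can shift by arm, and an apparent difference in local control can follow without any true effect. Section 13.1 treats a final one-sided p<0.10 as grounds for a phase III trial, so a false signal would have a direct consequence. The futility look in 13.4 uses intracranial response, which the same PI determines. Once an adjudicator has been unblinded, it cannot be undone.

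**Working it through.** **1. Can the plan, followed exactly, unblind the PI?** No stated figure decides this, so the sections are set side by side.

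| Link | Source | Finding |
|---|---|---|
| MRI before and after the first infusion | 5.1; section 10 calendars | Every patient |
| Active agent visible and retained in lesions | 2.2, 2.3 | Stated |
| Placebo carries no gadolinium | 8.1.10 | Saline |
| PI to remain blinded | 4.1, 5.1, 11.1.5 | Stated aim |
| PI is sole final adjudicator | 11.1.5, 11.1.7 | Stated |
| Images or reports withheld from the PI | whole protocol | No such text |
| Infusion-day scans excluded from the fused set | 11.1.3 | No such text |
| Reader of these scans | whole protocol | Not stated |
| Standard contrast on the infusion day | 5.1 | Named only for the planning MRI |

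Access is realistic. The PI enrols patients (5.1) and reviews contours and plans to credential treating physicians (5.8). The links support *can be unblinded*. The last two rows prevent *will be unblinded*.

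**2. Event count for the illustration.** The protocol gives 474 metastases but no number of events. Inputs from 13.1: HR 0.60, one-sided alpha 0.10, power 90%, control recurrence 27.5% at one year, 2.8 years of accrual, 6 months of minimum follow-up, 20% and 33% inflation.

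- Schoenfeld: 4(1.2816+1.2816)²/(ln 0.60)² = 100.7, so 101 events.
- Freedman: [(1+0.60)/(1−0.60)]² × (1.2816+1.2816)² = 105.1, so 106 events.
- Control hazard: −ln(1−0.275) = 0.3216 per year. With exponential times and uniform accrual, the event probability is 1 − e^(−0.5λ)(1−e^(−2.8λ))/(2.8λ). This gives 0.439 for control and 0.298 for AGuIX, mean 0.3686.
- Freedman count: 106/0.3686 = 287.6 metastases; 287.6/0.8 × 1.33 = 478, against the stated 474. Using × 1.2 in place of /0.8 gives 459.

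The design is close to reproducible and is not in dispute. About 101 to 106 effective events is a fair basis.

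**3. Illustration of bias.** Assumption, not in the documents: AGuIX has no effect, and a share r of AGuIX-arm recurrences is called necrosis, with no such shift in the control arm. The apparent HR is then about 1−r, and with D effective events

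P(one-sided p<0.10) = Φ( √(D/4) × |ln(1−r)| − 1.2816 ).

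For r = 10% and D = 106: √26.5 = 5.148; 5.148 × 0.1054 = 0.542; Φ(0.542 − 1.282) = 0.230.

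| r | Apparent HR | D = 101 | D = 106 |
|---|---|---|---|
| 0% | 1.00 | 10% | 10% |
| 5% | 0.95 | 15.3% | 15.4% |
| 10% | 0.90 | 22.6% | 23.0% |
| 15% | 0.85 | 32.1% | 32.8% |
| 20% | 0.80 | 43.6% | 44.7% |

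D is held fixed, although relabelling would remove a few events. A shift in the opposite direction would hide a benefit instead.

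**The case against.** The protocol obliges the PI to stay blinded, and nothing says that the PI views the infusion-day scans. Three further points limit how far the argument can go.

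- **Contrast.** If standard gadolinium is also given that day, the arms may look more alike. Section 11.1.1 asks for a T1 post sequence on all MRIs, which might be read to reach these scans. A reader might infer from 2.2 and 2.3 that the scan pair reveals the arm in every patient; those sections support visibility and retention, not identification in each case.
- **Fusion.** Section 11.1.3 concerns consistent measurement over the study and does not name the infusion-day scans. Reading it as an order that the PI inspect them goes beyond the text.
- **Baseline.** Section 11.1.3 wants baseline evaluations close to treatment start, and one might infer that baseline falls on a scan where the arms differ. The pre-infusion scan is from the same day and precedes any study agent, so the arms cannot differ on it. The calendars also list volumetric imaging under baseline.

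On size, the 90% accuracy quoted in 2.1 and 5.1 has no direction and no split by arm. Ordinary error of 10% would exist under perfect blinding, so it does not support a 10% one-way shift.

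These points stand as limits. They do not supply the missing safeguard: contrast is not specified as a masking measure, and a duty to remain blinded does not control access to images. Two secondary endpoints in 13.6, time to radiation necrosis and RECIST-based local recurrence, bear on the question but do not settle it. A necrosis imbalance could be a real effect or a biased call, and under 11.1.7 the PI determines recurrence throughout.

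**Conclusion.** The point holds as a gap in the blinding procedures. Section 5.1 aims to blind the PI completely and makes that blinding central to the primary endpoint, yet it schedules an image that can show the allocation and leaves it open to the adjudicator. Unmasking is possible, not certain in every patient, because readership and contrast on the infusion day are not stated.

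The documents do not fix the size. Under the one-way relabelling assumed above, at 5% to 20%, the false-positive chance would rise from 10% to about 15% to 45%. This range shows sensitivity and is not an estimate of what will happen. The point belongs in the protocol, not a statistical analysis plan, because 5.1 and 11.1.3 are where blinding and image evaluation are set.

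**What to change.** Amend 5.1 and 11.1.3 to state that:

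1. The post-infusion images and reports from the infusion day are withheld from the study PI as endpoint adjudicator until the endpoint data are locked.
2. These images are excluded from the fused set used for response and recurrence.
3. For patients whom the PI treats, any clinically needed finding from the scan goes through the separate covering team that 5.1 already uses for minor infusion reactions. This widens that team's present remit and should be written down.
4. Baseline lesion measurements come from a scan obtained before any study infusion, either the planning MRI or the pre-infusion MRI.

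Optionally, add a supportive analysis that counts every lesion meeting the size criterion in 11.1.5 as a failure, whatever the attributed cause. It also counts true necrosis and could penalise a radiosensitiser, so it cannot replace the primary analysis or cure unblinding.

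The cost is amendment wording, an image-access restriction and the PI's loss of the post-infusion scan. Access by other treating physicians for clinical care need not change. The optional analysis uses data already collected.
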